**Table 2 Steps for Calculating SF/RB Subscore**

Timepoint	Scenarios to calculate SF/RB Subscore
Baseline	
Scenario 1 Bowel preparation date (prior to an endoscopy) is assigned as the ‘anchor’ date. Three days daily diary data collected from patient’s e-diary between Day -22 and the day prior to the anchor date will be selected to calculate SF/RB scores. Daily dairy days selected closest to the anchor date will be selected first

	
Scenario 2 Bowel preparation date (prior to an endoscopy) is assigned as the ‘anchor’ date. If fewer than three days of daily diary data are available between Day –22 through to the day prior to the anchor date, then additional daily diary data collected post endoscopy starting with the score recorded 2 days after the endoscopy but prior to the randomization/enrollment will be selected to calculate SF/RB scores. Examples of this scenario are illustrated (see Appendix 3).

	
Scenario 3 Randomization/Enrollment Date is assigned as the ‘anchor’ date, if endoscopy did not occur between Day -21 and day prior to randomization/enrollment date. Three days worth of diary data prior to the ‘anchor’ date will be selected to calculate SF/RB scores. Daily dairy days selected closest to the anchor date will be selected first

Post Baseline	
Scenario 1 Bowel preparation date (prior to an endoscopy) occurring within 7 days prior to the visit date is assigned as the ‘anchor’ date. Three daily diary days collected within the 7 days prior to post baseline visit date will be selected, to calculate SF/RB scores. Daily dairy days selected closest to the anchor date will be selected first. Visit date is the day the PGA assessment is collected.
 
Scenario 2 Bowel preparation date (prior to an endoscopy) is assigned as the ‘anchor’ date. Three daily diary days collected within the 7 days prior to post baseline visit date will be selected, to calculate SF/RB scores. Daily dairy days selected closest to the anchor date will be selected first.
 
If further days are required, data collected +2 days after endoscopy within the 7 days prior to visit date will be used. Visit date is the day the PGA assessment is collected.

	
Scenario 3 Visit date is assigned as the ‘anchor’ date. Three daily diary days collected within the 7 days prior to post baseline visit date will be selected, to calculate SF/RB scores. Daily dairy days selected closest to the anchor date will be selected first.

SF= stool frequency; RB= rectal bleeding; PGA= Physician’s Global Assessment.

The change from baseline in the SF subscore and RB subscore at Week 6 between the treatment arms will be reported for GA28950, GA28949 and GA28948 studies. This data is considered non-parametric and will be reported using RANK analysis of covariance (ANCOVAs).

#### **4.4.2.1.2 Endoscopy**

Endoscopy= Assessment of segments from 3 locations (Colon Descending, Colon Sigmoid, Rectum).

Each location is scored using the following criteria:

### **Endoscopic Subscore 0–3**

- 0= Normal or inactive disease
- 1= Mild disease (erythema, decreased vascular pattern, mild friability)
- 2= Moderate disease (marked erythema, lack of vascular pattern, friability, erosions)
- 3= Severe disease (spontaneous bleeding, ulceration)

At baseline all segments are reviewed and scored and the worst score from the three segments is recorded as the endoscopy subscore. At baseline the endoscopy score is collected – 16 to –4 days prior to Day 1, however for analyses purposes, any endoscopy collected prior to randomization/enrollment date will be used as the baseline endoscopy score. All assessments are performed via video and assessed by both a local reader and a central reader; adjudication process is applied if required (see Section 3.2).

Post baseline the endoscopic score is the worst score of all segments which have been assessed at baseline, if the baseline endoscopy score had Sigmoid colon score  $\leq 1$ . If at baseline the sigmoid colon score was  $\geq 2$ , the post baseline endoscopy score is the sigmoid colon score value. This methodology is called the Hybrid Sigmoid (HS) model and is used as the primary method for all analyses across all studies and throughout the project and study SAP documents the HS methodology will be used when calculating endoscopic subscore.

For mMCS (excluding friability from ES=1) the patient's endoscopic subscore will be updated from ES=1 (mild disease) to ES=2 (moderate disease) if friability is present for either central reader 1 or central reader 2 at any location. All other patients' endoscopic subscores will remain the same. For all other analyses in Table 3 using the endoscopic subscore, the definition with mild friability is considered within endoscopic subscore of 1, will be used.

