#### **4.4.4 Sensitivity Analyses**

To support the primary analyses the following sensitivity analyses will be conducted: definitions of partial Mayo Clinic Score (pMCS) and mMCS are included in the project SAP, Section 4.4.2.1.4.

- Proportion of patients in remission at Week 62 among clinical responders at Week 10 (remission derived using mMCS including mild friability in Mayo ES = 1)
- Proportion of patients in remission at Week 62 among clinical responders at Week 10 (remission derived using pMCS)
- Proportion of patients in remission at Week 62 among clinical responders at Week 10 (difference in proportions calculated using Fisher's exact test)
- Proportion of patients in remission (mMCS) at Week 62 among clinical responders (mMCS) at Week 10 (excluding friability from Mayo ES = 1)
- Proportion of patients in remission at Week 62 among clinical responders at Week 10 (Tipping Point Analysis)

All key secondary endpoints included in [Figure 2](#) which are calculated using MCS or the endoscopic subscore will be re analyzed as a sensitivity analyses using the modified Mayo Clinic Score (mMCS) excluding friability from ES = 1 or the endoscopic subscore excluding friability from ES = 1 if applicable. This analysis will be conducted on the mITT population and are listed below.

- Proportion of patients corticosteroid free remission at Week 62 (Off corticosteroid for at least 24 weeks prior to Week 62) in patients who were receiving corticosteroids at baseline (remission derived using the mMCS excluding mild friability in Mayo ES = 1)
- Proportion of patients with improvement of endoscopic appearance of the mucosa at Week 62 (endoscopic score excluding mild friability in Mayo ES = 1)
- Proportion of patients remission at Week 62 among patients in remission at Week 10 (remission at Week 10 and Week 62 derived using the mMCS excluding mild friability in Mayo ES = 1)

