**Table 3 Outcome Measures**

Outcome Measure	Definition
Mayo Clinic Score (MCS)	MCS (0–12) is a composite of 4 assessments, each rated from 0–3: stool frequency, rectal bleeding, endoscopy, and PGA
Partial Mayo Clinic Score (pMCS)	pMCS (0–9) is a composite of 3 assessments, each rated from 0–3: stool frequency, rectal bleeding, and PGA
Modified Mayo Clinic Score (mMCS)	mMCS (0–9) is a composite of 3 assessments, each rated from 0–3: stool frequency, rectal bleeding, and endoscopy
MCS Remission	MCS $\leq$ 2 with individual subscores $\leq$ 1 and a rectal bleeding subscore of 0
MCS Clinical Remission	MCS $\leq$ 2 with individual subscores $\leq$ 1
MCS Clinical Response	MCS with $\geq$ 3-point decrease and 30% reduction from baseline as well as $\geq$ 1-point decrease in rectal bleeding subscore or an absolute rectal bleeding score of 0 or 1
pMCS Remission	pMCS $\leq$ 2, with, rectal bleeding score of 0, PGA 0–1 and stool frequency subscore 0–1
mMCS Remission (excluding friability from ES=1)	mMCS $\leq$ 2, with, rectal bleeding score of 0, endoscopy 0–1 and stool frequency subscore 0–1 (Friability must be Absent for ES=1)
mMCS Remission (including friability in ES=1)	mMCS $\leq$ 2, with, rectal bleeding score of 0, endoscopy 0–1 and stool frequency subscore 0–1
pMCS Clinical Remission	pMCS $\leq$ 2, with, rectal bleeding score of 0–1, PGA 0–1 and stool frequency subscore 0–1
mMCS Clinical Remission (excluding friability from ES=1)	mMCS $\leq$ 2, with, rectal bleeding score of 0–1, endoscopy 0–1 and stool frequency subscore 0–1 (Friability must be Absent for ES=1)
mMCS Clinical Remission (including friability in ES=1)	mMCS $\leq$ 2, with, rectal bleeding score of 0–1, endoscopy 0–1 and stool frequency subscore 0–1
pMCS Clinical Response	A decrease in the pMCS of at least 2 points and at least 30% improvement from baseline, with an accompanying decrease in the rectal bleeding score by at least one point or an absolute rectal bleeding score of 0 or 1.
mMCS Clinical Response (excluding friability from ES=1)	A decrease in the mMCS of at least 2 points and at least 30% decrease (improvement) from baseline, with an accompanying decrease in the rectal bleeding score by at least one point or an absolute rectal bleeding score of 0 or 1. (Friability must be Absent for ES=1)

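### In the friability-excluded mMCS analyses, friability in segments that do not supply the hybrid endoscopic score can still raise a sigmoid score of 1 to 2

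*SAP*

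**What the plan says.** Project SAP Section 4.4.2.1.2 scores three locations: descending colon, sigmoid colon and rectum. After baseline it applies the Hybrid Sigmoid model. If the baseline sigmoid score was 2 or more, "the post baseline endoscopy score is the sigmoid colon score value". If it was 1 or less, "Post baseline the endoscopic score is the worst score of all segments which have been assessed at baseline". The section adds that "throughout the project and study SAP documents the HS methodology will be used when calculating endoscopic subscore". Protocol Section 4.5.1.4 and Appendix 4 likewise use the sigmoid score after baseline when the baseline sigmoid score is 2 or 3.

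The next paragraph of the SAP section gives the rule for mMCS with friability excluded. A score of 1 becomes 2 "if friability is present for either central reader 1 or central reader 2 at any location". For everyone else, "All other patients' endoscopic subscores will remain the same". It then says that all other Table 3 analyses keep mild friability within score 1.

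Table 3 of the project SAP defines the variants by the condition "Friability must be Absent for ES=1" and names no segment.

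Study SAP Section 4.4.4 uses the friability-excluded mMCS in three places: a sensitivity analysis of the primary endpoint (with Week 10 responders also defined by mMCS), corticosteroid-free remission, and remission at Week 62 among Week 10 remitters. It also lists "Proportion of patients with improvement of endoscopic appearance of the mucosa at Week 62 (endoscopic score excluding mild friability in Mayo ES = 1", which is not an mMCS endpoint.

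**The concern.** When the baseline sigmoid score is 2 or 3, the hybrid model leaves the rectum and descending colon out of the post-baseline score. The friability rule brings them back, but only for patients whose sigmoid score is exactly 1. Two patients with the same rectal finding can then be classified differently, and a patient whose scored segment meets the Table 3 condition can still be failed.

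These analyses are labelled as excluding friability from score 1. If their results differ from the versions that keep friability in score 1, a reader will attribute the difference to friability. Part of it could come from a partial return to scoring segments that the hybrid model leaves out, and the outputs as planned would not separate the two.

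**Working it through.** The plan states no figure on this point, so there is none to reproduce. The check is one of logic.

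**Step 1: two patients.** Both have a baseline sigmoid score of at least 2. Both have a rectum scored 1 with friability at Week 62 and a normal descending colon. Patient A has sigmoid score 1 without friability. Patient B has sigmoid score 0.

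| Friability-excluded score | Patient A | Patient B |
|---|---|---|
| Hybrid score, upgrade limited to the scored segment | 1 | 0 |
| Worst of all segments, upgrade for friability anywhere | 2 | 2 |
| Rule as written | 2 | 0 |

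Table 3 requires an endoscopic score of 0 or 1 for mMCS remission. As written, A cannot be a remitter and B can. The written rule gives neither the first row nor the second.

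**Step 2: how general this is.** Assume friability occurs only in a segment scoring at least 1, and that all three segments were assessed at baseline. Each segment then has 7 states: score 0 without friability, and scores 1, 2 or 3 each with or without it. Three segments give 7 × 7 × 7 = 343 patterns.

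- Baseline sigmoid 2 or 3: the any-location and scored-segment rules differ when the sigmoid is 1 without friability and at least one other segment is friable. Four of the 7 states have no friability, so the count is 7 × 7 − 4 × 4 = 33 of 343.
- In the same group, sigmoid 0 with friability elsewhere is left at 0 in another 33 of 343.
- Baseline sigmoid 1 or less: the two rules differ in 0 of 343, because every segment already enters the score.

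These are counts of logical patterns, not patient frequencies.

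**Step 3: direction.** The rule only raises scores, so at Week 62 it can only remove remitters. In two of the analyses it also acts at Week 10, on mMCS response or mMCS remission, and so can change who is in the denominator. The direction of change in the resulting proportion is therefore not fixed there.

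**Step 4: size.** With a fixed denominator, the fall in the Week 62 remission rate is the remission rate multiplied by three shares:

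- the share of remitters with baseline sigmoid 2 or 3;
- the share of those with endoscopic score 1;
- the share of those with friability only outside the sigmoid.

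The documents give none of the three.

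**The case against.** The strongest reply is that requiring no visible friability in any segment before accepting a mild score is a coherent, conservative definition, prespecified and applied to blinded central reads. It is also fair that ignoring the rectum when the sigmoid is 0 is how the hybrid model works in every analysis, so part of the contrast between A and B belongs to that model. Both points stand. The SAP could keep the any-location rule if it presented it as a separate, stricter definition. It does not. It says the hybrid method governs the endoscopic subscore throughout, then departs from it without comment.

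Several stronger readings are tempting but not supported:

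- **That these analyses were designed to isolate friability.** The SAP says only that they support the primary and key secondary analyses. Using mMCS already drops the Physician's Global Assessment, and the primary sensitivity analysis also redefines Week 10 response.
- **That most patients are scored on the sigmoid alone.** Eligibility requires an endoscopic subscore of at least 2, but at baseline that is the worst segment's score. The share with baseline sigmoid 2 or 3 is not stated.
- **That the any-location rule certainly covers endoscopic improvement.** Section 4.4.2.1.2 states it for mMCS only.
- **That the friability flag should come from the reader whose score was adopted.** Project SAP Section 3.2 takes a median that includes the local read. With central 0, local 1 and central 2, the adopted score of 1 is the local reader's, and the rule uses friability from central readers only. Such a requirement could leave no usable flag.

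**Conclusion.** The inconsistency is real and sits within one section of the project SAP. It arises only for patients with a baseline sigmoid score of 2 or 3 whose post-baseline sigmoid score is 1 without friability. It affects three supportive analyses: the friability-excluded mMCS sensitivity analysis of the primary endpoint, and the mMCS re-analyses of corticosteroid-free remission and of remission among Week 10 remitters.

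A reader might infer that the primary result or the multiplicity-controlled tests are at risk. They are not, because those analyses keep mild friability within score 1. A reader might also infer a definite loss in remission rate, or a bias between arms. Neither can be shown from the documents. The size is unknown, and the only firm statement on direction is that at Week 62 the rule moves patients towards non-remission. To say that patients are misclassified is right only relative to the SAP's own hybrid definition.

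This rests on reading any location as any of the three segments that the section has just listed, which is its plain meaning.

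**What to change.** In project SAP Section 4.4.2.1.2, tie the upgrade to the scored segment. For example: in the friability-excluded analyses, an endoscopic subscore of 1 becomes 2 if central reader 1 or central reader 2 records friability in a segment that supplies the Hybrid Sigmoid score, meaning the sigmoid colon if its baseline score was 2 or 3, and otherwise the segments assessed at baseline. If the any-location version is wanted, report it separately and label it as a stricter definition, with a reason.

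In the same edit, reconcile the statement that the rule is for mMCS only with Table 3 and study SAP Section 4.4.4, which both use a friability-excluded endoscopic-improvement endpoint, and say which upgrade rule that endpoint follows.

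The cost is a short text change and one change to a derivation. No new data should be needed: segments are scored separately, and the current rule already refers to friability by location. The Independent Review Charter should confirm that the flag is held by segment. The project SAP is shared by five studies, so the change must be checked against each one that uses the variant, and made before these outputs are run.

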#### **4.4.2.1.3 Physician's Global Assessment**

The PGA will be provided by the investigator as a score of 0 to 3. The status is based on the physician's overall rating of the patient's disease activity, given endoscopy, stool frequency, rectal bleeding, abdominal pain, well-being, fecal continence, observations, and physical exam findings.

#### **Physician's Global Assessment**

- 0= Normal (Subscores are 0)
- 1= Mild disease (Subscores are mostly 1s)
- 2= Moderate disease (Subscores are 1 to 2)
- 3= Severe disease (Subscores are 2 to 3)

#### 4.4.2.1.4 Outcome Measures Derived from the MCS

The outcome measures calculated using the MCS or a selection of components from the MCS are detailed in [Table 3](#).

**Table 3 Outcome Measures**

Outcome Measure	Definition
Mayo Clinic Score (MCS)	MCS (0–12) is a composite of 4 assessments, each rated from 0–3: stool frequency, rectal bleeding, endoscopy, and PGA
Partial Mayo Clinic Score (pMCS)	pMCS (0–9) is a composite of 3 assessments, each rated from 0–3: stool frequency, rectal bleeding, and PGA
Modified Mayo Clinic Score (mMCS)	mMCS (0–9) is a composite of 3 assessments, each rated from 0–3: stool frequency, rectal bleeding, and endoscopy
MCS Remission	MCS $\leq$ 2 with individual subscores $\leq$ 1 and a rectal bleeding subscore of 0
MCS Clinical Remission	MCS $\leq$ 2 with individual subscores $\leq$ 1
MCS Clinical Response	MCS with $\geq$ 3-point decrease and 30% reduction from baseline as well as $\geq$ 1-point decrease in rectal bleeding subscore or an absolute rectal bleeding score of 0 or 1
pMCS Remission	pMCS $\leq$ 2, with, rectal bleeding score of 0, PGA 0–1 and stool frequency subscore 0–1
mMCS Remission (excluding friability from ES=1)	mMCS $\leq$ 2, with, rectal bleeding score of 0, endoscopy 0–1 and stool frequency subscore 0–1 (Friability must be Absent for ES=1)
mMCS Remission (including friability in ES=1)	mMCS $\leq$ 2, with, rectal bleeding score of 0, endoscopy 0–1 and stool frequency subscore 0–1
pMCS Clinical Remission	pMCS $\leq$ 2, with, rectal bleeding score of 0–1, PGA 0–1 and stool frequency subscore 0–1
mMCS Clinical Remission (excluding friability from ES=1)	mMCS $\leq$ 2, with, rectal bleeding score of 0–1, endoscopy 0–1 and stool frequency subscore 0–1 (Friability must be Absent for ES=1)
mMCS Clinical Remission (including friability in ES=1)	mMCS $\leq$ 2, with, rectal bleeding score of 0–1, endoscopy 0–1 and stool frequency subscore 0–1
pMCS Clinical Response	A decrease in the pMCS of at least 2 points and at least 30% improvement from baseline, with an accompanying decrease in the rectal bleeding score by at least one point or an absolute rectal bleeding score of 0 or 1.
mMCS Clinical Response (excluding friability from ES=1)	A decrease in the mMCS of at least 2 points and at least 30% decrease (improvement) from baseline, with an accompanying decrease in the rectal bleeding score by at least one point or an absolute rectal bleeding score of 0 or 1. (Friability must be Absent for ES=1)
mMCS Clinical Response (including friability in ES=1)	A decrease in the mMCS of at least 2 points and at least 30% decrease (improvement) from baseline, with an accompanying decrease in the rectal bleeding score by at least one point or an absolute rectal bleeding score of 0 or 1.
Improvement in endoscopic appearance of the mucosa (including friability in ES=1)	Endoscopy subscore $\leq$ 1

Endoscopic Remission (including friability in ES=1)	Endoscopy subscore=0
Improvement in endoscopic appearance of the mucosa (excluding friability from ES=1)	Endoscopy subscore ≤ 1 (Friability must be Absent for ES=1)

ES= Endoscopic Subscore; PGA=Physician's Global Assessment.

Endoscopy Score=1 includes mild friability criteria unless identified in the description of an endpoint above.

#### 4.4.2.2 Histologic Endpoints

For each patient, scanned images of hematoxylin and eosin stained slides of FFPE sigmoid colon biopsies are assessed by the same pathologist from among a small pool of central readers. Details of the reading process are included in Section 3.2. Each slide image is evaluated using two histologic scoring systems: NHI (Appendix 4) and Geboes Grading Scale (Appendix 5). A third score, the RHI, is derived from selected components of Geboes Grading Scale (Appendix 5).

All histologic endpoints will be evaluated only on patients who have documented neutrophilic inflammation at baseline. Neutrophilic Inflammation will be defined using the scoring system used within the analysis. The main analysis of each histologic endpoint will be conducted on the basis of NHI scoring system, and sensitivity analyses will be conducted using RHI and Geboes Grading Scale (Table 4). This data was not collected in the GA29103 study.

**Table 4 Histologic Endpoints**

Feature or Outcome	Description	Definition for each scoring system		
		NHI	RHI	Geboes Grading Scale
	Indication of neutrophilic inflammation	NHI > 1	RHI > 3	Geboes 2B.1–2B.3 or 3.1–3.3 or 4.1–4.3 or 5.1–5.3
Histologic remission	Resolution of neutrophilic inflammation	NHI ≤ 1	RHI ≤ 3 and Geboes 2B.0 and 3.0	Geboes 2B.0 and 3.0, and 4.0, and 5.0

NHI=Nancy Histological Index; RHI=Robarts Histopathological Index.

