#### **4.1.2.3 Histology-Evaluable Population**

The histology-evaluable patients will include all patients in the maintenance mITT population, who have documented neutrophilic inflammation at baseline. For the main analysis based on NHI, neutrophilic inflammation is characterized by NHI greater than 1. Sensitivity analyses will be based on the Robarts Histopathological Index (RHI) and Geboes Grading Scale. Definitions for neutrophilic inflammation and histologic remission under these alternative histologic scoring systems are provided in Table 3 of the project SAP.

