## Appendix 5 Geboes Grading Scale and Robarts Histopathological Index

### Geboes Grading Scale: Grades and Subgrades

Grade 0: Structural (architectural change)	Grade 3: Neutrophils in epithelium
0.0 No abnormality	3.0 None
0.1 Mild abnormality	3.1 < 5% crypts involved
0.2 Mild-moderate diffuse/multifocal abnormalities	3.2 < 50% crypts involved
0.3 Severe diffuse/multifocal abnormalities	3.3 > 50% crypts involved
Grade 1: Chronic inflammatory infiltrate	Grade 4: Crypt destruction
1.0 No increase	4.0 None
1.1 Mild but unequivocal increase	4.1 Probable—local excess of neutrophils in part of crypt
1.2 Moderate increase	4.2 Probable—marked attenuation
1.3 Marked increase	4.3 Unequivocal crypt destruction
Grade 2A: Eosinophils in lamina propria	Grade 5: Erosion or ulceration
2A.0 No increase	5.0 No erosion, ulceration or granulation tissue
2A.1 Mild but unequivocal increase	5.1 Recovering epithelium + adjacent inflammation
2A.2 Moderate increase	5.2 Probable erosion—focally stripped
2A.3 Marked increase	5.3 Unequivocal erosion
Grade 2B: Neutrophils in lamina propria	5.4 Ulcer or granulation tissue
2B.0 None	
2B.1 Mild but unequivocal increase	
2B.2 Moderate increase	
2B.3 Marked increase	

Source: [Geboes et al. 2000](#).

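### Project SAP Table 4: the Geboes baseline rule omits subgrade 5.4, and the RHI baseline rule does not mirror its remission rule, so a few biopsy patterns fall out of the histology sensitivity denominators

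*SAP*

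**What the plan says.** Project SAP Section 4.4.2.2 sets the denominator: "All histologic endpoints will be evaluated only on patients who have documented neutrophilic inflammation at baseline". It adds that "Neutrophilic Inflammation will be defined using the scoring system used within the analysis". NHI carries the main analysis; RHI and Geboes are sensitivity analyses. Study SAP Section 4.1.2.3 builds the histology-evaluable population on the same condition, namely mITT patients "who have documented neutrophilic inflammation at baseline".

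Table 4 of the project SAP gives a baseline definition and a remission definition for each system:

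- **NHI:** baseline NHI > 1; remission NHI ≤ 1.
- **Geboes:** baseline "Geboes 2B.1–2B.3 or 3.1–3.3 or 4.1–4.3 or 5.1–5.3"; remission "Geboes 2B.0 and 3.0, and 4.0, and 5.0".
- **RHI:** baseline RHI > 3; remission "RHI ≤ 3 and Geboes 2B.0 and 3.0".

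Appendix 5 of the project SAP lists the Geboes subgrades. Grades 2B, 3 and 4 end at .3. Grade 5 has one more level, "5.4 Ulcer or granulation tissue". Section 3.2 counts 5.3 and 5.4 alike as evidence of erosion or ulceration, and the RHI formula in Appendix 5 gives 5.4 the highest erosion score, 3.

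**The concern.** The baseline row of Table 4 decides who is counted, and the remission row decides who succeeds. For NHI the two rows are exact complements: a patient not in remission at baseline is by definition eligible. For Geboes and RHI they are not, so a biopsy can be too active to count as remission yet not active enough to be admitted.

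In the Geboes column the omission looks like a drafting slip. The other three grades stop at .3, the same ending was used for grade 5, and no reason is given for admitting 5.1 (recovering epithelium) but not 5.4. In the RHI column, the remission rule adds an explicit no-neutrophil condition, which has an effect only because RHI ≤ 3 can coexist with neutrophils. The baseline row, labelled as indicating neutrophilic inflammation, has no matching condition.

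At stake is the purpose of these analyses: to show whether the histologic remission result depends on the scoring system. If the denominators also shift through wording gaps, part of any difference between systems is an artefact. A programmer must either apply the literal rule and drop an ulcerated biopsy, or correct it silently and depart from the prespecified text.

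**Working it through.** **Inputs.** Baseline and remission rules are from Table 4. Subgrade ranges are from Appendix 5: grades 1, 2B, 3 and 4 take values 0–3, and grade 5 takes values 0–4. The RHI weights are 1 for chronic infiltrate, 2 for lamina propria neutrophils, 3 for epithelial neutrophils and 5 for erosion or ulceration, where 5.0 scores 0, 5.1 or 5.2 scores 1, 5.3 scores 2 and 5.4 scores 3.

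**Reproducing the plan's figure.** The maximum RHI is 1×3 + 2×3 + 3×3 + 5×3 = 3 + 6 + 9 + 15 = 33 and the minimum is 0, matching the stated range of 0–33.

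**Geboes.** Grades 2B, 3, 4 and 5 give 4×4×4×5 = 320 possible profiles.

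- The baseline rule fails only when 2B, 3 and 4 are all 0 and grade 5 is 5.0 or 5.4. That is 2 profiles, so 320 − 2 = 318 qualify.
- Of those 2, the one with 5.0 is remission. The other (2B.0, 3.0, 4.0, 5.4) meets neither definition.
- Profiles with 5.4 number 4×4×4 = 64, and 63 of them still qualify through grade 2B, 3 or 4.
- The lost profile has RHI between 0 + 15 = 15 and 3 + 15 = 18, depending on the chronic infiltrate, so it enters the RHI analysis. With an ulcer it would be NHI 4 under the index in protocol Appendix 12, so it also enters the main analysis.

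**RHI.** Grades 1, 2B, 3 and 5 also give 320 profiles. Any grade 5 finding adds at least 5, so RHI ≤ 3 requires 5.0 and chronic + 2×(2B) + 3×(grade 3) ≤ 3. Seven profiles satisfy this, so 320 − 7 = 313 meet the baseline rule.

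- Four have 2B.0 and 3.0 (chronic 0, 1, 2 or 3) and are remission.
- Three have neutrophils and meet neither rule:
  - chronic 0, 2B.1, 3.0: RHI = 0 + 2 = 2
  - chronic 1, 2B.1, 3.0: RHI = 1 + 2 = 3
  - chronic 0, 2B.0, 3.1: RHI = 0 + 3 = 3

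All three qualify under the Geboes baseline rule through 2B.1 or 3.1.

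**After the correction.** With 5.1–5.4 in the Geboes list, the unclassified Geboes profiles fall from 1 to 0. With RHI entry defined as RHI > 3, or 2B.1 or higher, or 3.1 or higher, the unclassified RHI profiles fall from 3 to 0. In neither system does a profile meet both definitions, before or after the change.

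**The case against.** The strongest objection concerns RHI. Nothing in the documents requires entry and remission rules to be complements. Section 4.4.2.2 lets each system supply its own meaning of neutrophilic inflammation, and for RHI that meaning is RHI > 3. A patient with RHI 2 or 3 already meets the numerical half of RHI remission before treatment, so leaving that patient out is defensible. This stands in part: the RHI mismatch is an inconsistency with the row's label and with the added neutrophil condition in the remission rule, not a breach of a stated rule.

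For Geboes, one could argue that an ulcer without neutrophils is not neutrophilic inflammation. That does not explain the text, because the same list admits 5.1 to 5.3 without any neutrophil finding.

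Three stronger readings are tempting and are not supported:

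- A reader might infer that ulcerated patients are excluded from the Geboes analysis. The criterion is a chain of alternatives, and 63 of the 64 profiles with 5.4 still enter.
- A reader might infer that patients are certainly lost. The documents give no baseline histology distribution, and profile counts are not patient frequencies.
- A reader might infer a biased comparison or undefined outcomes. Eligibility is fixed on biopsies taken before randomization and applies alike to both arms. At Week 62, a biopsy that does not meet the remission rule is simply not in remission.

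**Conclusion.** The point holds in a narrow form. The Geboes baseline rule is wrong as written: it omits 5.4, and one profile (5.4 with 2B.0, 3.0 and 4.0) is left out of the Geboes sensitivity analysis although it is not in Geboes remission. Secondarily, the RHI baseline rule leaves out three minimal-activity patterns with neutrophils, at RHI 2, 3 and 3. The two gaps do not overlap: the ulcer-only profile enters the RHI analysis, and the three RHI patterns enter the Geboes analysis.

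The size in patients is unknown and may be zero. The main NHI analysis of histologic remission is unaffected, because its definitions are already complements. The conclusion rests on reading Table 4 and Appendix 5 literally. It needs no assumption about how often the patterns occur. This is a clean-up of sensitivity analysis definitions, not a threat to any primary or key secondary result.

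**What to change.** In project SAP Table 4:

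1. Change the last Geboes baseline range from 5.1–5.3 to 5.1–5.4.
2. Define RHI baseline inflammation as RHI > 3, or Geboes 2B.1 or higher, or Geboes 3.1 or higher, so that it is the exact complement of RHI remission. If entry at RHI > 3 alone is intended, say so and give the reason.

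In the same revision, correct study SAP Section 4.1.2.3, which sends the reader to Table 3 of the project SAP for these definitions; they are in Table 4.

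The cost is three text edits and the matching change to the population flags. No new data or re-reading of slides is needed, since every subgrade involved is already scored. Because Table 4 sits in the project SAP, the correction also serves the other studies that use it.
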